Protocol

Disseminating Public Health Evidence to Support Prevention and Control of Diabetes Among Local Health Departments

NCT03211832

Updated October 11, 2021

A Stepped Wedge Cluster Randomized Controlled Trial

We will conduct a stepped wedge cluster randomized controlled trial of 12 local health departments (LHDs) in Missouri to evaluate the effectiveness of active D&I approaches on perceived individual and organizational capacity for evidence-based decision making in prevention of diabetes and other chronic diseases.

LHDs will be randomly assigned to three groups that crossover to receive the intervention with measurements at 8-month intervals. No LHDs receive the intervention at baseline. All participating 12 LHDs will receive the intervention, however, for varying durations; group 1 crosses over from control, i.e., usual practice to receive the intervention activities first and for a total of 24 months, group 2 crosses over second and receives the intervention for 16 months, and group 3 crosses over last and receives the intervention activities for 8 months. The intervention activities include a flexible "menu" of D&I approaches that account for local contextual and organizational factors. Dissemination strategies are designed to build workforce and organizational capacity, and may include training in evidence-based public health, technical assistance through a knowledge broker, providing targeted messages/emails with a short summary of the research and actions that might be taken based on the evidence, and organizational changes to assist agency leadership in prioritizing, incentivizing and incorporating the use of EBPPs. LHD practitioners can choose intervention activities from this "menu". This "menu" approach avoids the pitfalls of a "one-size-fits-all" process that is unlikely to be effective across the 12 participating LHDs. Therefore, this study will not attempt to evaluate a single D&I intervention activity but will pursue active, multi-modal approaches, since these are supported in the literature.

Local Health Department Enrollment

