Of the twelve LHDs selected, at least 3 will come from LHDs in counties with high diabetes disparity (highest tertile). Once all LHDs are recruited, each will be randomly assigned to one of three groups with four LHDs to a group. At least one LHD from high diabetes disparity will be randomly assigned to each group. Each group of LHDs will cross over to the intervention at 8-month intervals. To account for varying sample sizes for small versus large LHDs, we will limit our sample to LHDs with at least 5 employees working in or supporting chronic disease control and on the upper end no more than 22 individuals in larger LHDs. We will also include an additional 5-10 individuals (an average of 8) from partner agencies in each local community that include non-governmental organizations (e.g., local hospital, American Diabetes Association) and governmental organizations outside of the health sector (e.g., universities, parks/recreation, schools).

LHD selection will be based in part on the total number of full-time equivalent (FTE) employees (number of FTEs increases with size of population served by LHD), number of employees working in or supporting diabetes or chronic disease control, and diabetes burden, specifically mortality rate for diabetes as underlying cause (a measure of health disparity). Of the 12 LHDs selected and recruited, at least three will come from LHDs in counties from the highest tertile of mortality rate for diabetes as underlying cause. To be eligible, LHDs are required to have ≥ 5 employees working in or supporting diabetes or related areas in chronic disease control, which includes program areas of diabetes prevention and management, obesity prevention, physical activity, nutrition, cardiovascular health, school health, and cancer screenings. In addition, each LHD must have a designee to work with the study team on aspects of the intervention. LHDs will be assigned to one of three groups (four LHDs to each group) using simple random concealed allocation performed by the statistician.

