LHDs with a total number of FTEs ≥ 35 or serving a population of $\geq 200,000$ are anticipated to have an adequate number of employees working in diabetes and chronic disease control. The project manager (RP) contacted directors at LHDs with 25-34 FTEs and serve a population of $<200,000$ (8 LHDs) to determine if their LHD has ≥ 5 employees working in diabetes prevention and management, obesity prevention, physical activity, nutrition, cardiovascular health, or cancer screenings; 5 of the 8 LHDs met this criterion. Of eligible LHDs (17 of 115 LHDs), those with the greatest diabetes burden (i.e., in the highest tertile for mortality rate for diabetes as underlying cause) followed by LHDs with the largest total number of FTEs employees will be contacted and recruited. Random assignment of the first 12 selected LHDs to groups will be performed. The principal investigator will invite local health directors from each selected LHD to have their employees working in diabetes and chronic disease control participate in the study. If any LHD declines, the next LHD according to total number of FTE employees will be selected. All employees working in or supporting diabetes and chronic disease control in participating LHDs will be invited into the study (complete listing), and a purposive sample of individuals from partner agencies (other governmental and non-governmental) in each LHD local community will also be invited. LHDs' key partners will be recruited into the study with the help of the chronic disease managers and other practitioners. We anticipate a range of 5 to 22 participants from the LHDs, coupled with staff from partner agencies for an average of 22 per jurisdiction.

Participants will be diabetes and chronic disease control directors, program managers and staff, and leadership from recruited LHDs in Missouri as well as staff from their key partner agencies. It is anticipated the participants will be from diverse backgrounds including health educators, epidemiologists, community health nurses, and persons with business backgrounds.

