factor analysis using data from all four time points according to standard procedures demonstrated adequate fit and strict measurement invariance of the factor structure used for the national survey in an earlier study phase. We used linear mixed-effect regression models for each outcome with LHD and Participant entered as random intercepts, trial mode (control or intervention) as fixed effect, and time as a categorical fixed effect. Public health degree, years worked in the public health field, job position category and accreditation status were entered as fixed effects. Kenward-Rogers approximations will be used to determine significance of fixed effects, a common approach in fitting restricted maximum likelihood models in order to produce acceptable Type 1 error. Where models violated assumptions of homoscedasticity, robust models will be approximated. Survey data will be cleaned initially in SPSS and then managed and analyzed in R.

Table. Summary of individual and organizational capacity building (intervention) activities

| Domain | Activity | Description |
|----------------------------------|--|--|
| Accreditation | Accreditation preparations | Local health assessment and plan, formalized decision making, documentation of evidence, documentation reviews, site visit, approval |
| Access to scientific information | Targeted messages | Participants will receive an email indicating that a systematic review related to diabetes or chronic disease control is available |
| Workforce development | Evidence-based decision making (EBDM) training (dissemination workshops) | In-state, in-person multi-day training in EBDM skills, 9 modules, as initial study intervention (this is the kick-off activity for the entire study) |
| | Supplemental brief EBDM skill trainings | Provided by study team or state chronic disease unit, in-person or webinar, as part of this study, with 3 states emphasizing evaluation skills |
| | Non-study national trainings | Hosted in-person EBDM-related skill trainings by national organizations and/or encouraged out-of-state training beyond those required by funders |
| | Quality improvement | Quality improvement or performance management trainings, guidance |
| | New employee EBDM orientation | Via archived webinars or course materials, facilitated discussions, meetings |

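### Allocation is constrained on high diabetes disparity but the outcome models omit that factor, which leaves a small chance error that one extra term removes

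*Combined protocol and SAP*

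**What the plan says.** In the combined protocol and SAP, the section on Local Health Department Enrollment uses diabetes disparity twice.

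- **Selection.** Of the twelve LHDs, "at least 3 will come from LHDs in counties with high diabetes disparity (highest tertile") is the floor. Recruitment starts with these agencies: "Of eligible LHDs (17 of 115 LHDs), those with the greatest diabetes burden" are approached first, followed by the LHDs with most staff.
- **Allocation.** "At least one LHD from high diabetes disparity will be randomly assigned to each group". The same section also says: "LHDs will be assigned to one of three groups (four LHDs to each group) using simple random concealed allocation performed by the statistician". That sentence mentions no restriction.

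The Analysis Plan fits linear mixed models "with LHD and Participant entered as random intercepts, trial mode (control or intervention) as fixed effect, and time as a categorical fixed effect". The adjustment terms are given in one sentence: "Public health degree, years worked in the public health field, job position category and accreditation status were entered as fixed effects". Disparity status is not among them, and no reason is given. The number of high-disparity LHDs actually enrolled is not stated.

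**The concern.** A factor that constrains allocation would normally appear in the model, so that the analysis reflects the design. One might think this does not matter here, because each LHD moves from control to intervention and acts as its own control. That would be fully true if the model had LHD fixed effects. It has an LHD random intercept, and with an ICC of 0.009 to 0.027 the intercepts are shrunk strongly. The trial-mode estimate then takes part of its information from comparing LHDs with one another.

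Group 1 spends more waves under intervention than group 3. If high-disparity LHDs score differently at all times and happen to be more numerous in one of these two groups, some of that difference is read as an intervention effect. What is at stake is the accuracy of the estimate given the allocation that was drawn.

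**Working it through.** **Inputs from the documents.** There are 12 LHDs in three groups of four and four measurement waves. Groups 1, 2 and 3 have 3, 2 and 1 waves under intervention. The Power Analysis gives an ICC range of 0.009 to 0.027, built as 50% either side of a median; 0.018 × 0.5 = 0.009 and 0.018 × 1.5 = 0.027, so the median is 0.018. Its sample sizes also agree: 12 × 10 = 120 and 12 × 5 = 60. The stated power cannot be reproduced, because the percentage effects come without a mean or SD, but it is not needed here.

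**Assumptions.** Total SD 1; 10 respondents per LHD and wave; equal LHD sizes; known variance components; participant share of the non-LHD variance 0 (different people each wave) or 0.5 (same people return). K, the number of high-disparity LHDs, is not given.

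**1. Variance and pass-through.** For LHD-by-wave means, let σ² be the part that changes between waves and τ² the part that stays constant, with φ = τ²/(σ² + 4τ²). After centring trial mode within wave, its sum of squares is 8/3 + 8/3 = 16/3. The LHD totals are +1, 0 and −1 for groups 1, 2 and 3, with squares summing to 8. Hence

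- Var(trial mode) = σ² / (16/3 − 8φ)
- pass-through = (k1 − k3) × [σ²/(σ² + 4τ²)] / (16/3 − 8φ),

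where k1 and k3 are the numbers of high-disparity LHDs in the first and last groups. The middle group does not enter.

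| | Different people | Same people, share 0.5 |
|---|---|---|
| σ² | 0.982/10 = 0.0982 | 0.5 × 0.982/10 = 0.0491 |
| τ² | 0.018 | 0.018 + 0.0491 = 0.0671 |
| φ | 0.018/0.1702 = 0.106 | 0.0671/0.3175 = 0.211 |
| 16/3 − 8φ | 4.487 | 3.643 |
| SE | √(0.0982/4.487) = 0.148 | √(0.0491/3.643) = 0.116 |
| Pass-through per unit of k1 − k3 | 0.577/4.487 = 0.129 | 0.155/3.643 = 0.042 |

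**2. Between-LHD information.** With LHD fixed effects φ = 1/4 and the bracket is 10/3. The between-LHD share is 1 − 3.333/4.487 = 26%, or 1 − 3.333/3.643 = 8%. Over the plan's ICC range and 5 to 22 respondents per LHD it is 15-34% with different people, and 3-17% with within-person correlation 0.3 to 0.7.

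**3. Ceiling on the disparity effect.** A difference γ between high-disparity and other LHDs creates between-LHD variance γ²p(1 − p), with p = K/12. This cannot exceed the ICC, so γ ≤ √(0.018/[p(1 − p)]): 0.285 for K = 4, 0.272 for K = 5, 0.268 for K = 6. The ceiling is reached only if disparity explains every difference between LHDs.

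**4. Shift at that ceiling, and SE after adding the term.** Adding the indicator reduces the information by (k1 − k3)²/[(σ² + 4τ²) × 4K(12 − K)/12]. For 4/1/1 with different people: 4.487/0.0982 = 45.70; 45.70 − 9/(0.1702 × 12) = 41.29; SE 0.156.

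| Split | Pass-through (different / same) | Largest shift, SD | SE with term |
|---|---|---|---|
| 1/1/1, 1/2/1, 2/2/2 | 0 / 0 | 0 / 0 | 0.148 / 0.116 (1/1/1) |
| 2/1/1 | 0.129 / 0.042 | 0.037 / 0.012 | 0.149 / 0.116 |
| 3/1/1 | 0.257 / 0.085 | 0.070 / 0.023 | 0.151 / 0.117 |
| 4/1/1 | 0.386 / 0.127 | 0.103 / 0.034 | 0.156 / 0.118 |

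Splits weighted to the last group give the same size with opposite sign.

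**5. How often, under the restriction.**

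- K = 3: always 1/1/1, so no shift.
- K = 5: 624 allowed allocations. The first and last groups differ by two in 128 (20.5%) and not at all in 208 (33%).
- K = 6: 840 allowed allocations. They differ by two or more in 224 (27%), and by three in 32 (3.8%).

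The mean pass-through is zero. Its root mean square for K = 6 is 0.168 or 0.056, which at the ceiling is 0.168 × 0.268 = 0.045 SD or 0.056 × 0.268 = 0.015 SD.

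**6. If allocation was unrestricted.** With K = 3, a 1/1/1 split occurs in 64/220 = 29% of allocations. With K = 4, a 4/0/0 split would pass 4 × 0.129 × 0.285 = 0.147 SD (different people), about one SE, but all four fall in an end group in only 2/495 = 0.4% of allocations.

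**The case against.** The strongest reply is that nothing is wrong with the inference. Every LHD contributes both conditions ("All participating 12 LHDs will receive the intervention"). Unexplained differences between LHDs are what the random intercept represents, and they already enter the standard error, with Kenward-Roger inference. The restriction itself limits imbalance. The participant random intercept, and the planned fall from 10 to 5 subjects per LHD, point to a followed cohort, where the pass-through is only 0.04 per unit. Nothing in the documents links county diabetes mortality to staff-reported skills or culture. Staff numbers also drive selection and are not in the model either.

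Most of this stands. No Type I error problem is shown, and the same-people figures fit the plan better, although fresh contact lists at each wave leave room for turnover. Two points remain. Staff numbers guide selection only, whereas disparity also constrains allocation. And the term costs almost nothing.

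A reader might infer a larger problem from the share of uneven splits: with five such LHDs, 192/624 = 31% are 3/1/1 in some order, and with six, 624/840 = 74% are uneven. Those counts overstate it, since an excess in the middle group has no effect. A reader might also put the disparity effect at 0.3 SD. With five or six such LHDs, that exceeds the ceiling of about 0.27 SD at ICC 0.018.

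**Conclusion.** The point holds as a minor improvement. The allocation factor is missing from the model, and a difference in its count between the first and last groups passes partly into the trial-mode estimate. At ICC 0.018 and 10 per LHD and wave, the worst split under the restriction moves the estimate by about 0.7 of a standard error with different people (0.103/0.148) and 0.3 with the same people (0.034/0.116). Both figures assume that disparity explains all between-LHD variance. Typical shifts are far smaller.

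A reader might conclude that the omission biases the trial. The documents do not support that: the error averages zero over the randomisation and is zero with three high-disparity LHDs, one per group. Nor do they show that more than three were enrolled; recruitment order makes it possible, but no count is given.

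The sizes rest on the assumed respondent numbers, participant share and K. The conflict between the two allocation statements rests on no assumption.

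**What to change.** 1. Reconcile the two allocation statements in the enrollment section: say whether allocation was restricted on disparity and, if so, how. Give the number of high-disparity LHDs in each group.
2. Add high-disparity status (highest mortality tertile, yes or no) as an LHD-level fixed effect in every outcome model. It is useful under either reading of the allocation.

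The factor is known for every LHD before allocation, so no data need collecting. The cost is one LHD-level degree of freedom. At ICC 0.018 and 10 per LHD and wave, the standard error rises by about 0-2% for splits up to 3/1/1 (0.148 to 0.151 at most) and about 5% at worst for 4/1/1 (0.148 to 0.156). The term removes a disparity difference that is constant over time; it does not remove a disparity-by-time trend.
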